^a Dosing calculations should be based on the body weight assessed at baseline. It is not necessary to re-calculate subsequent doses if the participant weight is within 10% of the weight used to calculate the previous dose. All doses should be rounded up or to the nearest milligram per institutional standard.

Table 5.1-6: Follow-Up Assessments - All Subjects (CA209358)

| Procedure | X, Follow-Up ^a Visits X01 and X02 | Follow-Up Assessments for Neoadjuvant Cohort Subjects 4, 8, and 12 Months Post-Surgery ^b | S, Survival Follow-Up ^c Visits | Notes |
|---|--|--|---|--|
| Safety Assessments | | | | |
| Targeted Physical Examination | X | | | 
Lymph node areas (eg, submandibular, cervical, supraclavicular, axillary, or inguinal lymph node), and abdominal organs (eg, spleen, liver).
 
To assess for potential late emergent study drug related issues
 |
| Adverse Events Assessment | X | | X | NSAEs and SAEs must be collected up to 100 days after study drug discontinuation. SAEs that relate to any later protocol specified procedure must be collected. |
| Review of Medical History and Subsequent Cancer Therapy Information | X | X | X | |
| Laboratory Tests | X | | | CBC with differential and platelet count, BUN or serum urea level, serum creatinine, sodium, potassium, calcium, magnesium, phosphorus, chloride, bicarbonate or total CO ₂ (if locally available), amylase, lipase, glucose, AST, ALT, total bilirubin, alkaline phosphatase, LDH, albumin.. |
| Thyroid Function Testing | X | | | TSH (reflex to free T3 and free T4 if abnormal result) |
| Pregnancy Test | X | | | Serum or urine |

Table 5.1-6: Follow-Up Assessments - All Subjects (CA209358)

| Procedure | X, Follow-Up ^a Visits X01 and X02 | Follow-Up Assessments for Neoadjuvant Cohort Subjects 4, 8, and 12 Months Post- Surgery ^b | S, Survival Follow-Up ^c Visits | Notes |
|---|--|--|--|---|
| Efficacy Assessments | | | | |
| Radiographic Tumor Assessment | See Note | X | See note | Only for subjects without progression and no longer on study therapy |
| Spiral CT/MRI | | | | See Table 5.4.1-1 for Spiral CT/MRI. For subjects in the neoadjuvant cohort, radiographic tumor assessment should be at 4 mo, 8 mo and 12 mo post-surgery. ^b Subjects with a history of brain metastasis may have surveillance MRI approximately every 12 weeks or sooner if clinically indicated |
| Outcomes Research Assessments | | | | |
| EORTC QLQ-C30 | X | | | |

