| EQ-5D | X | | X | EQ-5D during the survival follow-up will be assessed during a clinic visit or via a phone contact |
| Pharmacokinetic/Immunogenicity Assessments | | | | |
| PK Samples | X | | | See Table 5.5-1 , Table 5.5-2 , Table 5.5-3 , Table 5.5-4 , Table 5.5-5 , and Table 5.5-8 for PK and Immunogenicity Sampling |
| Immunogenicity samples | X | | | |

Table 5.1-6: Follow-Up Assessments - All Subjects (CA209358)

| Procedure | X, Follow-Up ^a Visits X01 and X02 | Follow-Up Assessments for Neoadjuvant Cohort Subjects 4, 8, and 12 Months Post- Surgery ^b | S, Survival Follow-Up ^c Visits | Notes |
|---|--|--|--|---|
| Additional Exploratory Biomarker Testing | | | | |
| Serum | See Note. | | | Collection of Biomarker samples at time of progression is optional. See Table 5.6.9-1 , Table 5.6.9-2 , and Table 5.6.9-3 , and Table 5.6.9-4 for Biomarker Sampling Schedule. |
| Whole Blood | | | | |
| Tumor Biopsy | | | | |
| PMBC | | | | |
| Plasma | | | | |
| Subject Status | | | | |
| Survival Status | X | X | X | Every 3 months after X02; may be accomplished by visit or phone contact, to update survival information and assess subsequent anti-cancer therapy. |

^a X visits occur as follows: X01 = 35 days \pm 7 days from last dose or from the date decision is made to discontinue subject from the study (only applicable for early treatment discontinuation), X02 = 80 days \pm 7 days from X01. Neoadjuvant cohort subjects will have these visits labeled as E01 (35 days \pm 7 days from last dose) and E02 (80 days \pm 7 days) visits in the CRF. For neoadjuvant cohort subjects receiving nivolumab as part of the post-standard of care, X01 and X02 visits will be completed after the last dose

^b Follow-Up Assessments for Neoadjuvant Cohort Subjects, 4, 8, and 12 Months Post-Surgery, may occur \pm 7 days from scheduled time point. 4 Month Post-Surgery may occur \pm 3 weeks from scheduled time point. Neoadjuvant Cohort. E02 and E03 follow-up can occur at the same time.

^c S, Survival Follow-Up visits continue every 3 months after X visits.

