| Time On Study | Assessment Frequency | Assessment Window |
|---------------|--|--|
| Screening | At screening (within 35 days of first dose) | Within 35 days of first dose |
| Pre-Surgery | Day 29 (within 7 days prior to the planned surgery date) | within 7 days prior to the planned surgery date |
| Post-Surgery | Months 4, 8, and 12 ^a | Months 4 (within ±3 weeks), 8, and 12 ^b |

^a Any images obtained prior to Month 4 as standard of care should also be assessed.

^b 4-Month Post-Surgery Assessments for Neoadjuvant Cohort Subjects may occur ± 3 weeks from scheduled time point. Follow-up assessments 8 and 12 Months Post-Surgery may occur ± 7 days from the scheduled time point. Neoadjuvant Cohort E02 and E03 Follow Up may occur at same time.

For the Metastatic Cohorts (monotherapy and combination therapy), baseline tumor assessments should be performed within 35 days prior to the first dose. Subjects will then be evaluated for tumor response beginning 8 weeks from the date of first dose (± 1 wk.), then every 8 weeks (± 1 wk.) thereafter up to 48 weeks, then it will be every 12 weeks (± 2 weeks) until disease progression is documented, or when treatment is discontinued (whichever occurs later).

For the Neoadjuvant Cohort, a Day 29 tumor scan is required for within 7 days prior to the planned surgery date.

For Neoadjuvant Cohort subjects who progress to unresectable recurrent or metastatic disease within 1 year of surgical resection or chemotherapy/radiation and receive nivolumab, a baseline tumor scan documenting progression is required prior to restarting nivolumab. Subjects will then be evaluated for tumor response beginning 8 weeks from the date of first dose of treatment (± 1 wk.), then every 8 weeks (± 1 wk.) thereafter up to 48 weeks, then it will be every 12 weeks (± 2 week) until disease progression is documented, or when treatment is discontinued, (whichever occurs later).

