- Recurrence-free survival (RFS), which is defined as the time from surgery to the date of recurrence(local, regional, metastasis, locally advanced unresectable recurrence, clinical or radiographic progression occurs after surgery) as determined by investigators, or death due to any cause, whichever occurs first. (Note: a subject who dies without reported recurrence will be considered to have recurred on the date of death.) For subjects who remain alive and whose disease has not recurred, RFS will be censored on the date of last evaluable disease assessment. Participants who did not have any post-surgery disease assessments and did not die will be censored on the surgery date. Further details on the censoring rules for consideration of subsequent therapies, will be described in the Statistical Analysis Plan (SAP).
- The proportion of treated subjects who experiences pathologic complete response will be used to determine pathologic response rate of tumors after two doses of neoadjuvant nivolumab in HPV positive and negative SCCHN, resectable Merkel Cell Carcinoma, and cervical, vaginal, or vulvar cancer. Pathological complete response (pCR) is defined as the absence of residual viable invasive cancer on hematoxylin and eosin evaluation of the complete resected tumor specimen and all sampled regional lymph nodes following completion of neoadjuvant systemic therapy.

Metastatic cohorts (monotherapy and combination therapies):

- The safety and tolerability objective will be measured by the incidence of adverse events, serious adverse events, deaths and laboratory abnormalities.
- Pre- and post-treatment EBV DNA levels will be collected in the subjects with EBV positive gastric cancer and nasopharyngeal carcinoma. The change in EBV DNA levels will be used to determine the effect of BMS-936558 (nivolumab). (Monotherapy cohort only)

Neoadjuvant and Metastatic cohorts (monotherapy and combination therapies):

- The PK samples collected will be used to determine summary measures of nivolumab, ipilimumab, BMS-986016 (relatlimab), and daratumumab exposures (see [Section 8.4.4](#))
- Exploratory endpoints for pharmacodynamics, outcomes research and immunogenicity are discussed in detail in [Sections 5.6, 5.7](#) and [5.8](#).

Other exploratory endpoints will be discussed in detail in the statistical analysis plan.

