4.3 Exploratory Endpoints

4.3.1 Neoadjuvant Cohort only

- The percent change from baseline of immune cells and the percent change from baseline of select immune activation/inhibitory molecules of viral-specific T cells in tumor specific subsets of nivolumab treated subjects will be evaluated. The percent change is the ratio of change from the baseline and baseline measurement.
- Recurrence-free survival (RFS), which is defined as the time from surgery to the date or recurrence (local, regional, metastasis, locally advanced unresectable recurrence, clinical or radiographic progression occurs after surgery) as determined by investigators, or death due to any cause, whichever occurs first. (Note: a subject who dies without reported recurrence will be considered to have recurred on the date of death.)

Table 4.3-1: Censoring scheme used in primary definition of RFS

Situation	Date of Recurrence or Censoring	Outcome
Recurrence (local, regional, metastasis, locally advanced unresectable recurrence, clinical/radiographic progression occurs after surgery)	Date of the earliest documented recurrence/progression after surgery	Event
Death without documented recurrence after surgery/biopsy	Date of death	Event
No post-surgery disease assessment and no death	Date of surgery	Censored
No recurrence and no death	Date of last evaluable disease assessment	Censored
New anticancer therapy ^a started without recurrence or death	Date of last evaluable disease assessment prior to or on the same date of initiation of subsequent therapy	Censored

^a Protocol allowed adjuvant therapy in SOC follow up phase is not counted as subsequent therapy.

Table 4.3.1-2: Censoring scheme used in sensitivity analysis of RFS

Recurrence (local, regional, metastasis, locally advanced unresectable recurrence, clinical/radiographic progression occurs after surgery)	Date of the earliest documented recurrence/progression after surgery	Event
Death without documented recurrence after surgery/biopsy	Date of death	Event
No post-surgery disease assessment and no death	Date of surgery	Censored
No recurrence and no death	Last known alive date	Censored
New anticancer therapy ^a started without recurrence or death	Date of last evaluable disease assessment prior to or on the same date of initiation of subsequent therapy	Censored

^a Protocol allowed adjuvant therapy in SOC follow up phase is not counted as subsequent therapy.

- Safety endpoints ([Section 7.6](#))

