7.5.3 Exploratory Analyses

7.5.3.1 Neoadjuvant Cohort only

- The percent change from baseline of immune cells and the percent change from baseline of select immune activation/inhibitory molecules of viral-specific T cells in tumor specific subsets of treated subjects will be evaluated. Change from baseline will be summarized using descriptive statistics (n, mean, standard deviation, median, first and third quartiles, minimum, maximum).
- The following analyses will be conducted for RFS in primary analysis and sensitivity analysis. RFS curves for each tumor type will be estimated using the Kaplan-Meier (KM) product limit method. Median RFS and the corresponding two-sided 95% confidence intervals using the log-log transformation will be computed. Survival rates at 3, 6, 9, 12 months will be estimated using KM estimates on the RFS curve for each tumor type. Minimum follow-up must be longer than the time point to generate the rate. Associated two-sided 95% CIs will be calculated. Primary RFS analysis should use censoring scheme listed in [Table 4.3-1](#). Sensitivity RFS analysis should use censoring scheme listed in [Table 4.3.1-2](#).
- The percent change in tumor volume from baseline after two doses of neoadjuvant nivolumab will be summarized using descriptive statistics (n, mean, standard deviation, median, first and third quartiles, minimum, maximum).
- Pathological complete response (pCR) rate will be summarized using all treated subjects who received surgery by a binomial response rate. The Clopper-Pearson method will be used to estimate the two-sided 95% confidence intervals. Summary of continuous % residual viable tumor (%RVT) results will be provided descriptively if the data is available.

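### In the primary neoadjuvant RFS analysis, scheduled censoring ends at about Month 12 but deaths count at any later date, so one late death can take the Kaplan-Meier curve to zero and set the median

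*SAP*

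**What the plan says.** **Events and censoring.** SAP 4.3.1 and Protocol 8.3.3 define RFS from surgery to recurrence or death. On deaths the SAP says: "a subject who dies without reported recurrence will be considered to have recurred on the date of death". Neither document limits how late that death may fall, or how long after the last disease assessment. On survivors the protocol says: "For subjects who remain alive and whose disease has not recurred, RFS will be censored on the date of last evaluable disease assessment". SAP Table 4.3-1, the primary scheme, follows the same rule.

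**Assessment schedule.** Protocol Table 5.4.1-2 gives the post-surgery imaging times as "Months 4, 8, and 12", with a window of 7 days either side at Month 12. Table 5.1-6 agrees: "For subjects in the neoadjuvant cohort, radiographic tumor assessment should be at 4 mo, 8 mo and 12 mo post-surgery". No later disease assessment is scheduled for this cohort.

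**Survival contact.** Table 5.1-6 continues it: "Every 3 months after X02; may be accomplished by visit or phone contact, to update survival information".

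**Reporting.** SAP 7.5.3.1 plans a Kaplan-Meier curve, rates at 3, 6, 9 and 12 months, and a median: "Median RFS and the corresponding two-sided 95% confidence intervals using the log-log transformation will be computed". The requirement that minimum follow-up exceed the time point is attached to the rates only. A sensitivity analysis (SAP Table 4.3.1-2) instead censors event-free survivors at "Last known alive date".

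**Timing.** The SAP's Schedule of Analyses, which still calls the endpoint PFS, places the analysis at least twelve months after the last subject's surgery or biopsy. Subjects operated on earlier will have more than 12 months of survival follow-up.

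**The concern.** Kaplan-Meier estimation needs the subjects at risk at a given time to represent everyone still event-free then. Here, survivors leave the risk set at their last assessment, while a subject who later dies stays in it until death. Whether a subject is at risk after Month 12 thus depends on the outcome itself. The death rule is harmless where scanning continues alongside death follow-up, as it does until progression in the metastatic cohorts. It misbehaves here because scheduled scanning stops and death ascertainment does not.

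At stake are the part of the curve beyond Month 12 and the reported median. Revised Protocol 07 replaced PFS by RFS as the better reflection of neoadjuvant efficacy. A cohort with about three quarters of its subjects event-free at a year could be reported with a finite median and a curve at zero because of one death.

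**Working it through.** The documents give no RFS rate, median or event count, so there is no stated figure to reproduce. The check applies the product-limit estimator to the plan's own rules.

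**Inputs from the documents:** 21 subjects per neoadjuvant tumor type (SAP section 5); last scheduled assessment at Month 12; death an event on its date; survivors censored at the last assessment. **Assumed:** all 21 have surgery, and there are no unscheduled later assessments.

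**Formula.** At each event time, S is multiplied by (1 − d/n), where d is the number of events and n the number at risk, including the subject having the event.

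**1. Worked example.** 5 events by Month 12, 15 survivors, 1 death at Month 20.
- S(12) = 16/21 = 76.2%.
- The 15 survivors are censored at Month 12, so 1 subject is at risk at Month 20.
- S(20) = 0.762 × (1 − 1/1) = 0, and the median is 20 months.
- Without that death, S stays above 50% and the median is not reached.
- Under the sensitivity scheme, if all 15 survivors are known alive beyond Month 20, 16 are at risk: S(20) = 0.762 × 15/16 = 71.4%, median not reached.

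**2. When the median moves.** With 10 early events, S(12) = 11/21 = 52.4%, and a single late death becomes the median. With 11, S(12) = 10/21 = 47.6%: the median was reached by Month 12 and does not move, although the curve still ends at zero. With 2 or 3 late deaths the risk sets are 2, 1 or 3, 2, 1. The last death gives S = 0, and one of the late deaths sets the median whenever S(12) exceeds 50%.

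**3. How often.** Let h be the yearly death rate without recorded recurrence after Month 12, with follow-up beyond Month 12 uniform over 0 to F years. A subject event-free at Month 12 then has an observed late death with probability q = 1 − (1 − e^(−hF))/(hF). With 12-month RFS of 75%, the chance of at least one late death among 21 is 1 − (1 − 0.75q)^21.

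| Follow-up beyond Month 12 | 3% per year | 5% | 10% |
|---|---|---|---|
| 0-12 months | 21% | 32% | 54% |
| 0-24 months | 37% | 54% | 78% |
| 0-36 months | 50% | 69% | 90% |

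For example, h = 0.03 and F = 1 give q = 0.0149 and 1 − (1 − 0.0111)^21 = 21%. Reading the rates as annual probabilities instead of hazards changes the last row to 51%, 69% and 91%. With 60% 12-month RFS, 3% per year and 0-12 months, the chance is about 17%.

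**The case against.** **A planned analysis already shows the problem.** SAP 7.5.3.1 requires the same curve and median under the sensitivity scheme, which largely avoids the collapse, so a reader would see both. This stands in part. Table 4.3-1 remains the primary analysis, and the sensitivity scheme treats time without assessment as free of recurrence. The two could report a median of 20 months and a median not reached, with no stated way to reconcile them.

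**The late risk set need not consist only of subjects who die.** Censoring is at the last evaluable assessment, not the last scheduled scan, and investigator-determined clinical recurrence counts as an event. Protocol 4.5 allows renewed nivolumab for recurrence within a year of surgery or of completing standard of care, whichever is later, so documented recurrences after Month 12 are foreseen. This stands and limits the claim. Such data would keep some subjects at risk longer, but only haphazardly. Some late deaths may also drop out because new anticancer therapy began first; Table 4.3-1 does not say which row takes precedence.

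**Follow-up is not indefinite.** A reader might infer that deaths accrue for years, since Protocol 3.1 mentions up to 5 further years of survival follow-up. That extension is tied to the OS analysis, and OS is an endpoint only for the metastatic cohorts. The end-of-study analysis in SAP 7.11 does not include RFS. The definition has no limit, but the data cut-off imposes one, so the shorter follow-up rows belong in the range.

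**RFS is exploratory.** This stands: the study is non-comparative, the cohort's primary endpoints are safety and surgery delay, and no decision rule uses median RFS.

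**Conclusion.** The mechanism holds for the primary scheme as written. Absent unscheduled later assessments or late documented recurrences, the last death after Month 12 takes the curve to zero. A late death also sets the median if at most 10 of 21 subjects have had an event by Month 12. The collapse follows from the rules; its frequency does not. The chance per tumor type runs from about 21-54% to about 50-90% according to follow-up length, and rests on an assumed 12-month RFS, late mortality and follow-up distribution that the documents do not give.

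A reader might infer that all the planned RFS results are biased. They are not: deaths after Month 12 leave the 3-, 6-, 9- and 12-month rates unchanged, and no primary conclusion depends on RFS. The damage is confined to the curve beyond Month 12 and the median. It should still be corrected, because it affects the primary RFS display and the remedy is cheap.

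**What to change.** In SAP 4.3.1 (Table 4.3-1) and 7.5.3.1:
- Apply a common administrative cut-off to primary RFS at Month 12 after surgery plus the 7-day window.
- Count recurrences and deaths as events only up to that cut-off.
- Censor every subject with a recurrence-free Month-12 assessment at that common time, so that small differences in scan date do not recreate the problem at the edge.
- Show the curve only to the cut-off, and give a median only if it is reached by then.
- Report later recurrences and deaths descriptively.

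Counting a death only when it falls within 4 months of the last assessment is not a substitute. In the example, a death at Month 14 would count with 1 subject at risk, so S would again fall from 76.2% to 0%, with a median of 14 months.

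The cost is SAP wording and one programming rule, with no new data. The downside is small: events after Month 12 leave the primary RFS analysis.

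### The only RFS sensitivity analysis censors no earlier than the primary one, so it can never be lower and cannot show whether missed assessments flatter RFS

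*SAP*

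**What the plan says.** SAP 4.3.1 gives two censoring tables for RFS in the neoadjuvant cohort. Their event rows are the same: investigator-determined recurrence, which includes "clinical or radiographic progression occurs after surgery) as determined by investigators", or death.

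The tables differ only for subjects with no recurrence and no death. Table 4.3-1 (primary) censors them at "Date of last evaluable disease assessment"; Table 4.3.1-2 (sensitivity) censors them at "Last known alive date".

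Two other rows matter and are the same in both tables. Subjects in the row "No post-surgery disease assessment and no death" are censored at surgery. Subjects who start new anticancer therapy are censored at "Date of last evaluable disease assessment prior to or on the same date of initiation of subsequent therapy"; a footnote exempts protocol-allowed adjuvant therapy.

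Protocol 8.3.3 has only the first rule: "For subjects who remain alive and whose disease has not recurred, RFS will be censored on the date of last evaluable disease assessment". It leaves to the SAP the censoring details for subsequent therapies.

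On follow-up, Protocol Table 5.4.1-2 schedules post-surgery scans at "Months 4, 8, and 12". Under Protocol Table 5.1-6, survival status is collected every 3 months and "may be accomplished by visit or phone contact, to update survival information"; the same sentence adds an assessment of subsequent anticancer therapy.

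SAP 7.5.3.1 plans Kaplan-Meier curves, the median, and rates at 3, 6, 9 and 12 months under each scheme. It names no other RFS sensitivity analysis and gives no reason for choosing this one.

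**The concern.** In RFS, the missing-data question is what happened to subjects whose disease assessments stopped early. The worry is that some recurred unseen, so that the primary estimate is too high. A useful sensitivity analysis lets the estimate fall if that is so.

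Table 4.3.1-2 works the other way. It keeps such subjects in the risk set, free of recurrence, up to a date supported by vital status and not by a disease assessment. A report could then state that RFS was robust in a sensitivity analysis when the only alternative examined could not have been worse. The sponsor adopted RFS in Revised Protocol 07 as the more clinically meaningful measure of neoadjuvant efficacy, so its one robustness check ought to be informative.

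**Working it through.** The documents state no RFS rate, event count or imaging dropout, so there is no plan figure to reproduce.

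**Direction.** The Kaplan-Meier estimate is S(t) = product over event times of (1 - d/n), with d events among n at risk.
- d is the same in both schemes.
- A subject assessed on a date is alive on that date, so the last known alive date is never earlier than the last evaluable assessment. Each n is equal or larger under the sensitivity scheme.
- Each factor (1 - d/n) is then equal or larger, so the sensitivity S(t) is at least the primary S(t) at every t.

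In 20,000 random datasets of 21 subjects, the sensitivity curve was below the primary in none and strictly above it somewhere in 17,149. The median was lower in none.

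**Constructed example, 21 subjects** (the neoadjuvant cohort size per tumor type). There are two recurrences at each of months 4, 8 and 12. Of the other 15 subjects, 6 stop scans after month 4, 3 after month 8, and 6 are scanned to month 12. All 15 are known alive at month 24.
- Primary at month 12: (19/21) x (11/13) x (6/8) = 57.4%.
- Sensitivity at month 12: (19/21) x (17/19) x (15/17) = 15/21 = 71.4%.
- At month 9: 76.6% against 81.0%.

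**Illustrative size.** Assume exponential recurrence with true 12-month rate S12, detection at the next scheduled scan, a share q who stop scans after month 4, no clinical detection afterwards, and last contact after month 12. Then S4 = S12^(1/3).
- Primary: S12, because stopping is unrelated to outcome.
- Sensitivity: (1 - q) x S12 + q x S4, because stoppers have no recorded event after month 4.
- Gap: q x (S4 - S12).
- First missed scan counted as an event: (1 - q) x S12.

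For S12 = 60%, S4 = 84.3% and the gap is 2.4, 4.9 or 7.3 points at q = 10, 20 or 30%. For 70%, S4 = 88.8% and the gap is 1.9, 3.8 or 5.6. For 80%, S4 = 92.8% and the gap is 1.3, 2.6 or 3.8.

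Simulation of 2,000 datasets of 21 subjects per setting, with last contact at months 15 to 24, agrees (12-month RFS, %):

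| True | q | Primary | Sensitivity | Missed scan = event |
|---|---|---|---|---|
| 60 | 10 / 20 / 30 | 60.2 / 60.2 / 60.2 | 62.6 / 65.0 / 67.5 | 54.3 / 48.2 / 42.1 |
| 70 | 10 / 20 / 30 | 70.1 / 70.0 / 70.0 | 71.9 / 73.8 / 75.7 | 63.2 / 56.2 / 48.9 |
| 80 | 10 / 20 / 30 | 80.0 / 79.9 / 80.1 | 81.3 / 82.6 / 84.0 | 72.1 / 64.1 / 55.9 |

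With q = 0 the primary and sensitivity 12-month rates are identical.

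The two directions need not be of similar size. At a true 80% with q = 10%, the planned sensitivity analysis differs from the primary by 1.3 points, while the lower bound is 80.0 - 72.1 = 7.9 points below it.

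**The case against.** **Late deaths.** The best defence is that death is an RFS event. After scans end, the primary scheme still counts deaths although event-free survivors have left the risk set. Suppose 21 subjects have recurrences at months 4, 4, 8, 8 and 12, one death at month 20, and 15 event-free subjects last scanned at month 12. At month 20 the primary risk set is that one subject, so the curve drops to 0 and the median is 20 months. With the 15 survivors known alive at month 24, the sensitivity curve is 15/21 = 71.4% and the median is not reached. Last-known-alive censoring is a reasonable response to that, and an upward move there is not necessarily bias. This stands.

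**Unscanned is not unobserved.** A reader might infer that a phone contact says nothing about recurrence. The documents do not support that. The contact also covers subsequent therapy, clinical recurrence counts as an event, subjects who start new therapy keep the primary censoring date, and subjects never assessed after surgery gain no time. If half of unscanned recurrences are found clinically and the true rate is 60%, the sensitivity estimate is about 61 to 64% over q = 10 to 30%, and the primary is itself low, at about 59 to 57%. With better detection, last-known-alive censoring may be the closer of the two. This also stands, and it makes the no-detection assumption upper-end.

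**Month 12.** A reader might infer that ending scans at month 12 inflates the reported rates. It does not: the latest reported rate is at month 12, and with complete scanning the 3- to 12-month rates are the same under both schemes.

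**Weight.** RFS is exploratory, the study is non-comparative, and no decision rule uses this result. With 21 subjects the binomial standard error at 60% is sqrt(0.6 x 0.4 / 21) = 10.7 points, more than any gap in the simulation. Close agreement also carries some information, since it suggests few long assessment gaps.

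None of this gives the plan an analysis that can move downward.

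**Conclusion.** The point holds in a limited form. The single planned RFS sensitivity analysis can equal or exceed the primary but never fall below it. It therefore cannot show whether missed assessments make RFS look too good. That follows from the two tables and needs no assumption about the data.

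The size does need assumptions. Under those listed, the upward gap at 12 months is about 1 to 7 percentage points, and it arises only if scans are missed within the first year. Later contacts affect the later curve and possibly the median. The documents give neither an RFS rate nor an imaging dropout rate, so this is an illustration and not a prediction.

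A reader might go further and infer that the primary RFS result is inflated by this rule. It is not: Table 4.3-1 follows Protocol 8.3.3 and is unaffected. The consequence is confined to how robustness is described for an exploratory endpoint, and the change is worth making because it is cheap.

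**What to change.** In SAP 4.3.1 and 7.5.3.1, add an RFS sensitivity analysis that can move downward. Either of these would do:
- an interval-censored RFS estimate; or
- a rule that counts the first missed scheduled scan with no later assessment as an event, labelled a lower bound because it is deliberately extreme (48.9% against a true 70% when 30% stop scans).

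If last-known-alive censoring is kept, for example because of deaths after scans end, give that reason, label it an optimistic (upper) bound, and do not leave it as the only sensitivity analysis.

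Do not simply put the last evaluable assessment into the row of Table 4.3.1-2. That row is the only difference between the tables, so the result would duplicate Table 4.3-1.

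The data are already collected. The cost is a little programming and a less favourable sensitivity figure for an exploratory endpoint.
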